5.5.9	Laboratory Data	36
5.6	General Principles	37
5.6.1	Pooling of Trial Sites	37
5.6.2	Handling of Drop-outs and Missing Values	38
5.6.3	Incomplete dates	38
5.6.4	Multiplicity adjustment	38
5.6.5	Treatment Labels	39
5.7	Changes to the analyses described in the protocol	40
	Appendix I	47
	Appendix II	67

Trial ID: LP0053-1004	Date: 15-JUL-2019	Version: 1.0 Page 6 of 177
------------------------------	--------------------------	-------------------------------

3 List of Abbreviations

ACTH	Adrenocorticotropic Hormone
AE	Adverse Event
ATC	Anatomical Therapeutic Chemical
BSA	Body Surface Area
CPM	Clinical Project Manager
CPMP	Committee for Proprietary Medicinal Products
CRA	Clinical Research Associate
CRF	Case Report Form
CRO	Contract Research Organisation
DK	Denmark
DLQI	Dermatology Life Quality Index
eCRF	Electronic Case Report Form
eDiary	Electronic Diary
EU	European Union
GCP	Good Clinical Practice
ICH	International Conference on Harmonisation
IEC	Independent Ethics Committee
IMP	Investigational Product
IRB	Institutional Review Board
m-PASI	Modified Psoriasis Area Severity Index
MedDRA	Medical Dictionary for Regulatory Activities
MMRM	Mixed effect Model Repeat Measurement
ML	Maximum Likelihood
PASI	Psoriasis Area Severity Index
PASI 75	A 75% reduction in the modified Psoriasis Area Severity Index
PGA	Physician's Global Assessment of Disease Severity
PRO	Patient Reported Outcome
PSI	Psoriasis Symptom Inventory
REML	Restricted Maximum Likelihood
SAE	Serious Adverse Event

SAP	Statistical Analysis Plan
SD	Standard Deviation
SGA	Subject's global assessment of disease severity
SOC	System Organ Class
SOP	Standard Operating Procedure
UNS	Unscheduled Visit

4 Introduction

The statistical analysis will be performed as outlined in the Clinical Trial Protocol including amendments. This statistical analysis plan, prepared before the unblinding of the trial, but after the blind review of the data, contains a more technical and detailed elaboration of some points in the statistical analysis described in the Clinical Trial Protocol. Deviations from the planned data presentation and analysis are also described in section [5.7](#). Furthermore, the analysis sets, which are to be used for the statistical analysis, are presented.

5 Statistical Analysis

5.1 Definition of trial periods

The trial periods are defined in [Table 1](#).

Table 1: Definition of trial periods

Trial period	Definition
Open-label phase	From the day of enrolment to the day before randomisation.
Randomised phase	From the day of randomisation to end of trial, both days included.
Maintenance phase	From the day of first exposure to maintenance IMP to the last day of exposure (rescue or maintenance IMP), both days included.
Follow-up phase	From the day after last application of maintenance or rescue IMP to end of trial.
Relapse period	Relapse is defined as a PGA score of at least 'mild' during the maintenance phase, for details on relapse see CTP section 6.14.1. A relapse period is defined from the relapse start day (included) to the

	visit date when relapse treatment is discontinued (not included).
Remission period	A remission period is a period where the subject is not in a relapse period within the maintenance phase.
Visit interval	The interval between two successive scheduled visits.

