6.1.2 Screening/Washout Phase

Prior to performance of any trial related procedure (including washout), signed informed consent must be obtained from the subject.

A washout period will have to be completed for subjects who are or have recently been treated with anti-psoriatic treatments or other relevant medication not permitted as defined by the exclusion criteria (see Section [7.3](#)). The washout is to ensure that no other treatment could interfere with the response obtained with the IPs in the trial. The duration of the washout period is limited for logistical reasons to a maximum of 4 weeks. Because the maximum washout is 4 weeks, subjects who have recently been treated with biologics that require more than a 4 week washout period (e.g. ustekinumab should not be used for 16 weeks prior to commencing the trial), will not be eligible for the trial unless they have been off-treatment for several weeks (e.g. at least 12 weeks for ustekinumab) prior to the eligibility evaluation.

Assessment of subject eligibility should be made at a Screening Visit, prior to commencing a washout period. Screening assessments and trial procedures to be performed at Screening Visit are outlined in Section 8. On completion of the washout period, confirmation of the subject's ongoing eligibility for the trial will be made at Visit 1.

However, if no washout is needed the subject can enter Visit 1 directly.

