10.9.2.4 Drug Accountability

The investigator is fully responsible for the 0.9% Sodium Chloride Injection, USP at the trial site. Dispensing of the 0.9% Sodium Chloride Injection, USP may be delegated, e.g. to a hospital pharmacy, as locally applicable. The person responsible for dispensing the 0.9% Sodium Chloride Injection, USP will be responsible for maintaining adequate control and for documenting all transactions. All 0.9% Sodium Chloride Injection, USP sourced locally by the investigator (or designee) will be fully documented by use of (internal) drug accountability forms. An inventory will be kept of all 0.9% Sodium Chloride Injection, USP dispensed for each subject in the trial. The batch number/lot number and expiry date of the 0.9% Sodium Chloride Injection, USP dispensed will be recorded. This inventory must be available for inspection at monitoring visits and will be checked to ensure correct dispensing of the 0.9% Sodium Chloride Injection, USP.

11 Statistical Methods

The trial consists of two different periods of treatment. The subjects are enrolled in the trial at baseline. The first 4 weeks of treatment after a subject is included in the trial will be denoted the open-label treatment phase. If the subject obtains treatment success (i.e., PGA score of 'clear' or 'almost clear' with at least 2-grade improvement from baseline) at the end of the open-label treatment phase, the subject is randomised. Otherwise the subject is discontinued from the trial. The second treatment period is denoted the maintenance phase. It starts at randomisation and ends at end of trial. The randomised maintenance treatment is twice weekly treatment with either LEO 90100 aerosol foam or LEO 90100 aerosol foam vehicle. Moreover, the subjects treated twice weekly with LEO 90100 aerosol foam is referred to as the active treatment group and those treated twice weekly with vehicle is referred to as the vehicle group.

Note that the maintenance phase consists of maintenance treatment as well as periods of 4 weeks treatment with rescue medication in case of relapse.

In the following when referring to visit it means scheduled visit although not explicitly stated.

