13.3 Source Data

For all data recorded, the source document must be defined in a source document agreement at each trial site. There must only be one source defined at any time for any data elements.

The trial monitor will check the eCRFs for accuracy and completeness by verifying data recorded in the eCRF against source data to ensure such records are consistent.

Source data should as a general rule be recorded in the subject's medical record or other defined document normally used at the trial site. Source data not normally collected as a routine part of the clinical practice at the site may be entered on a worksheet. Clinical assessments/safety evaluations must be signed by medically qualified (sub)investigators.

If the worksheet does not become part of the subject's medical record, the following should as a minimum be added to the subject's medical record:

- Date(s) of conducting the informed consent process (date of enrolment) including date of provision of subject information
- Subject ID

- Randomisation code number (if applicable)
- The fact that the subject is participating in a clinical trial in psoriasis vulgaris including treatment arms of LEO 90100 or vehicle for up to 56 weeks
- Other relevant medical information
- Allocated treatment once the randomisation code has been broken (if applicable)

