5.2 Trial Analysis Sets

The trial analysis sets are defined in [Table 2](#). The analysis sets are described in more detail in the Analysis Set Definition Document.

Table 2: Trial analysis sets

Analysis set	Definition
Enrolled subjects	All subjects enrolled (informed consent obtained) in the trial.
Open-label safety analysis set	All subjects exposed to LEO 90100 during the open-label phase.
Open-label HPA analysis set	All subjects in the open-label safety analysis set who provided consent for the Adrenocorticotrophic Hormone (ACTH) challenge test and underwent a Hypothalamic-Pituitary-Adrenal (HPA) axis test.
Full analysis set	All subjects randomised who had treatment success at randomisation, defined as PGA score of 'clear' or 'almost clear' with at least a 2-grade improvement from baseline. Subjects randomised without treatment success will be excluded from the full analysis set. This approach is in alignment with the ICH E9, since achieving treatment success is a major randomisation criterion measured prior to randomisation and therefore exclusion of such subjects will not introduce bias.
Per protocol analysis set	The per protocol analysis set will be defined by excluding subjects from the full analysis set as described in the protocol and in the Analysis Set Definition Document.
Safety analysis	All subjects exposed to IMPs following randomisation and with available

set	post-randomisation safety evaluations.
Randomised subjects	All subjects randomised to the maintenance phase.
HPA analysis set	All subjects in the safety analysis set who provided consent for the ACTH challenge test and underwent an HPA axis test.

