5.5.1 Exposure

Duration of exposure will be summarised as described in the protocol section 11.3.3.1. If the date of last application of IMP is missing, the date of last visit attended by the subject will be used instead.

Patient years of exposure during a trial phase will be calculated as exposure during the relevant phase (accounting for both maintenance and rescue IMP as relevant) divided by 365.25.

The amount of IMP used will be summarised for the open-label treatment phase. For each subject the amount of IMP used will be normalised by the length of the open-label phase.

The total amount of IMP used, and the amount of rescue IMP used will be summarised by treatment group for the maintenance phase. For each subject the total amount of IMP and the amount of IMP used will be normalised by the length of maintenance phase or the total time in relapse, respectively.

The amount of IMP used, and the amount of rescue will not be summarised for each visit interval as described in the protocol. Instead a cumulative plot of the amount of IMP used over time during the maintenance phase by each subject together with an average cumulative amount curve will be done for the safety analysis set. The cumulative amount of IMP for each subject will be normalised by time in the maintenance phase (in days). The cumulative

Trial ID: LP0053-1004	Date: 15-JUL-2019	Version: 1.0 Page 30 of 177
-----------------------	-------------------	--------------------------------

amount of IMP used up to each scheduled visit and the corresponding number of subjects contributing to these amounts will be tabulated by treatment group.

More details for the tables and listings can be found in [Appendix I](#) and [Appendix II](#).

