Shell 90: Duration of exposure during the maintenance phase: safety analysis set

LEO 90100 (n=xxx)	Vehicle (n=xxx)
Duration of exposure	
Number of days	xxx
Mean (SD)	xx.x (xx.x)
Median	xx.x
Q1;Q3	xx.x;xx.x
Min;Max	xx.x;xx.x

SD: Standard deviation, Q1: 1st quartile, Q3: 3rd quartile.

Shell 91: Amount of investigational medicinal product used during open-label treatment phase: open-label safety analysis set

Open-label LEO 90100 (n=xxx)	
Amount of IMP used	
Number of subjects	xxx
Mean (SD)	xx.x (xx.x)
Median	xx.x
Q1;Q3	xx.x;xx.x
Min;Max	xx.x;xx.x

SD: Standard deviation, Q1: 1st quartile, Q3: 3rd quartile.

The amount of IMP used is normalised by the number of days in the open-label phase for each subject.

Trial ID: **LP0053-1004**

Date: **15-JUL-2019**

Version: 1.0

Page 166 of 177

Shell 92: Amount of investigational medicinal product used during maintenance phase: safety analysis set

	LEO 90100 (n=xxx)		Vehicle (n=xxx)	
	Total IMP	Rescue IMP	Total IMP	Rescue IMP
Number of subjects	xxx	xxx	xxx	xxx
Mean (SD)	xx.x (xx.x)	xx.x (xx.x)	xx.x (xx.x)	xx.x (xx.x)
Median	xx.x	xx.x	xx.x	xx.x
Q1;Q3	xx.x;xx.x	xx.x;xx.x	xx.x;xx.x	xx.x;xx.x
Min;Max	xx.x;xx.x	xx.x;xx.x	xx.x;xx.x	xx.x;xx.x

SD: Standard deviation, Q1: 1st quartile, Q3: 3rd quartile.

The amount of IMP used for each subject is normalised by the number of days in the maintenance phase or number of days in remission, respectively.

Shell 93: Cumulative amount of investigational medical product used up to scheduled visits: maintenance phase safety analysis set

	LEO 90100 (n=xxx)	Vehicle (n=xxx)
Visit 3		
Number of subjects	xxx	xxx
Mean (SD)	xx.x (xx.x)	xx.x (xx.x)
Median	xx.x	xx.x
Q1;Q3	xx.x;xx.x	xx.x;xx.x
Min;Max	xx.x;xx.x	xx.x;xx.x
...		
Visit 15		
Number of subjects	xxx	xxx
Mean (SD)	xx.x (xx.x)	xx.x (xx.x)
Median	xx.x	xx.x
Q1;Q3	xx.x;xx.x	xx.x;xx.x
Min;Max	xx.x;xx.x	xx.x;xx.x

SD: Standard deviation, Q1: 1st quartile, Q3: 3rd quartile.

Shell 94: Serum-cortisol concentration at time 0 and at 30 and at 60 minutes after ACTH-challenge test by visit: open-label HPA analysis set

Open-label LEO 90100 (n=xxx)	
Visit 1	
0 min (before ACTH-challenge test)	
Number of subjects	xxx
Mean (SD)	xx.x (xx.x)
Median	xx.x
Q1;Q3	xx.x;xx.x
Min;Max	xx.x;xx.x
30 min after ACTH-challenge test	
Number of subjects	xxx
Mean (SD)	xx.x (xx.x)
Median	xx.x
Q1;Q3	xx.x;xx.x
Min;Max	xx.x;xx.x
60 min after ACTH-challenge test	
Number of subjects	xxx
Mean (SD)	xx.x (xx.x)
Median	xx.x
Q1;Q3	xx.x;xx.x
Min;Max	xx.x;xx.x
Visit 2	

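### The open-label amount of product per day is divided by a phase that can include washout days and has no end for treated subjects who are never randomised

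*SAP*

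**What the plan says.** SAP 5.1, Table 1, sets the open-label phase as "From the day of enrolment to the day before randomisation". SAP 5.5.1 uses that term as a divisor: "For each subject the amount of IMP used will be normalised by the length of the open-label phase". The footnote to Shell 91 in SAP Appendix II repeats the rule: "The amount of IMP used is normalised by the number of days in the open-label phase for each subject". Shell 91 is produced for the open-label safety analysis set, which is everyone exposed to LEO 90100 in that phase, randomised or not.

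The documents describe enrolment in two ways.

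- **Consent.** SAP 5.2, Table 2, describes the enrolled set as "All subjects enrolled (informed consent obtained) in the trial". The list of source data in protocol 13.3 includes "Date(s) of conducting the informed consent process (date of enrolment". Protocol 11.2 also ties enrolment to consent, together with registration in the trial.
- **Visit 1.** The introduction to protocol section 11 states: "The subjects are enrolled in the trial at baseline". It continues: "The first 4 weeks of treatment after a subject is included in the trial will be denoted the open-label treatment phase". Protocol 6.1.1 has eligible subjects enrolled to the open-label phase once screening is over.

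On the order of events, protocol 6.1.2 is clear: "Prior to performance of any trial related procedure (including washout), signed informed consent must be obtained from the subject". Protocol 7.8.1 allows a washout of up to 28 days. A footnote to the schedule in protocol 8.1 lets screening and Visit 1 fall on the same day when no washout is needed.

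**The concern.** The open-label phase is the once-daily treatment period, and grams per day is the SAP's only summary of how much product was used in it. A subject who consents, washes out and then starts treatment has days before Visit 1 on which no product was available. If those days enter the divisor, the result reflects washout length as well as use, and it errs in one direction only. Shell 91 shows only the normalised amount, so the table does not let a reader undo the effect.

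The second problem is separate. Randomisation requires treatment success at Week 4, and everyone else leaves the trial (protocol 6.1.3). For them there is no day before randomisation, yet Shell 91 includes them. Table 1 does not close their phase by another route, because its follow-up phase begins only after the last maintenance or rescue application, and these subjects have neither.

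**Working it through.** The documents give no open-label daily amount to reproduce, so the check is of the rule itself.

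**Inputs.** Treatment lasts 28 days (protocol 3.3.3), with a visit window of ±4 days (protocol 8.1). Washout is 0 to 28 days (protocol 7.8.1 and 8.1). Fourteen and 28 days correspond to the 2-week topical and 4-week general systemic exclusion periods in protocol 7.3. Use of about 30 g/week, taken from the earlier 4-week trials in protocol 3.2, serves for illustration: 30 × 4 = 120 g in 28 days.

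**Start date, reading enrolment as consent.** Reported g/day equals true g/day × treatment days / (washout days + treatment days).

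| Washout days | Factor | Reported g/day for 120 g |
|---|---|---|
| 0 | 28/28 = 1.00 | 120/28 = 4.29 |
| 7 | 28/35 = 0.80 | 120/35 = 3.43 |
| 14 | 28/42 = 0.67 | 120/42 = 2.86 |
| 21 | 28/49 = 0.57 | 120/49 = 2.45 |
| 28 | 28/56 = 0.50 | 120/56 = 2.14 |

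At 28 washout days the visit window moves the factor from 24/52 = 0.46 to 32/60 = 0.53.

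**Average effect.** The share of subjects needing washout is not stated. As an assumption, let a share f have the full 28 days and the rest none. With equal use in both groups, the mean factor is 1 − 0.5f: 0.875 at f = 0.25, 0.75 at f = 0.50, 0.625 at f = 0.75 and 0.50 at f = 1.

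**Start date, reading enrolment as Visit 1.** The factor is 1.00 and nothing is diluted.

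**End date, either reading.** Protocol 11.1 assumes 48% treatment success, so 100% − 48% = 52% of treated subjects have no randomisation day. On the planned 832 that is 0.52 × 832 ≈ 433. The randomised counts in SAP Table 8 sum to 132 + 55 + 52 + 68 + 56 + 68 + 114 = 545. If 48% had held, 545/0.48 − 545 ≈ 590 treated subjects would have no end date.

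**What else uses the phase length.** The Shell 44 footnote divides the open-label PSI area by days in the open-label phase, while SAP 5.4.4.4 divides by the time from Visit 1 to Visit 2. Open-label AE rates use patient-years of exposure (SAP 5.5.1 and 5.5.3), so washout days do not enter them.

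**The case against.** The strongest reply is that enrolment in Table 1 means Visit 1. Protocol 6.1.1 and the introduction to section 11 say so in substance, and protocol 7.5 separates screened from enrolled subjects. Shells 1 and 3 tabulate open-label withdrawals among enrolled subjects with visit categories only for Visit 1 or Visit 2, which leaves no place for someone who drops out during washout. SAP 5.7 lists no change to the open-label phase, and the Table 2 wording describes a population, not a start date. SAP 5.5.1 itself introduces the open-label amount as belonging to the treatment phase.

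This stands as far as it goes: the start date is ambiguous, and dilution cannot be stated as a certainty. It does not remove the problem, because the only gloss of enrolled in the SAP is consent and protocol 13.3 equates the two dates.

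A second reply is that a date that does not exist cannot be used, so programming would have to resolve the end date. That is likely, but the SAP does not say how. Its last-visit rule replaces a missing last application date for duration of exposure; it does not set the length of the phase.

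A third reply concerns the remedy. Adverse events are assigned to periods by onset date (SAP 5.5.3). Redefining the Table 1 row as first to last application would leave events between the last open-label dose and randomisation in no period. This is correct, and it limits the remedy to the divisor.

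A reader might also infer that open-label use will be reported at half its true level overall, or that the table is planned as a check against the weekly maximum. The documents support neither. One half is about the largest effect for a single subject, and no section states that comparison as the table's purpose.

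**Conclusion.** Wrong as written, with low priority because the table is descriptive.

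- **Start of the phase.** The definitions conflict. On the consent reading, g/day is understated by 33% after 14 days of washout and by about 50% after 28 days (54% if Visit 2 is at the early edge of its window). It is not understated for subjects screened and started on the same day. On the Visit 1 reading there is no understatement. The average effect cannot be given without the share needing washout.
- **End of the phase.** It is undefined for treated subjects never randomised on either reading. The figure of about 52% rests on the protocol's planning assumption, not on trial data.
- **Reach.** The effect is confined to Table 1-37 (Shell 91) and the Shell 44 footnote. Open-label AE rates and the primary and secondary efficacy tests are untouched.

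**What to change.** Leave the open-label row of SAP Table 1 in place for assigning adverse events. In SAP 5.5.1 and the Shell 91 footnote, replace the divisor with each subject's open-label duration of exposure: first to last open-label application, counting both days, for randomised and non-randomised subjects alike. Where the last application date is missing, apply the last-visit rule already in SAP 5.5.1. Change the Shell 44 footnote to the Visit 1 to Visit 2 period used in SAP 5.4.4.4.

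The cost is one derived variable and some SAP wording. The application dates are already needed for duration of exposure under protocol 11.3.3.1. The amount and PSI summaries will have slightly different divisors, so each footnote should state its own.
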